9.0 Reportable Events and Data Safety Monitoring

We have developed a Data and Safety Monitoring Plan and Board to ensure the safety of participants and to monitor participant recruitment, accrual, randomization, and retention; treatment delivery and fidelity; and data collection and quality.

Data and Safety Monitoring Plan (DSMP)

Adverse Event Monitoring

As we are doing in our ongoing eIMPACT Trial (see C2), we will systematically identify potential adverse events (AEs): (a) by conducting Eskenazi Health EMR searches every 6 months (before DSMB meetings) for all emergency department visits, hospitalizations, and deaths that occurred among randomized patients and (b) by reviewing responses on a self-report questionnaire assessing for the occurrence of any potential adverse events since the pre-treatment visit administered at the post-treatment visit. The eIMPACT-DM depression clinical specialist will also receive alerts through the Eskenazi Health EMR when any randomized patient has a new emergency department visit or hospitalization, which will provide real-time monitoring. Finally, any potential adverse events spontaneously reported by participants (e.g., during a study visit or call) will be evaluated. We will fully investigate, rate, and prepare a Case Report Form for those events that are plausibly related to depression, depression treatment, suicidal ideation, or any study procedures and for all deaths. For all other captured events (emergency department visits or hospitalizations typically for chronic medical conditions that are unrelated to study involvement), we will provide frequency counts for the eIMPACT-DM and Active Control arms. We will fully investigate these events only if there is evidence of group imbalance. It is worth noting that that: (a) we are delivering safe and established depression interventions, (b) we are not delivering any new or experimental interventions or restricting usual care, and (c) all study procedures are noninvasive (except for the blood draw) and standard.

Adverse Event Rating and Reporting

All events plausibly related to depression, depression treatment, suicidal ideation, or any study procedures and all deaths will be promptly rated using the anticipation, severity, and attribution scales below. These ratings will be included in the Case Report Form for the adverse event signed by [name] (principal investigator) and [name] (trial psychiatrist).

Anticipation

1. Anticipated
2. Unanticipated

Severity

1. Mild: Awareness of sign or symptom but easily tolerated
2. Moderate: Interference with normal daily activities
3. Severe: Inability to perform normal daily activities
4. Life-Threatening: Immediate risk of death from the reaction as it occurred

Attribution

1. Definite: Adverse event clearly related to study involvement
2. Probable: Adverse event likely related to study involvement
3. Possible: Adverse event may be related to study involvement
4. Unlikely: Adverse event doubtfully related to study involvement
5. Unrelated: Adverse event clearly not related to study involvement

All AEs that meet the IUPUI IRB prompt reporting requirements (unanticipated; definitely, probably, or possibly related to study involvement; and suggest that the research places participants or others at a greater risk of harm than was previously known or recognized) will be immediately reported the IUPUI IRB, DSMB, CRC Research Subject Advocate, and NIH. All severe or life-threatening AEs will be immediately reported to and reviewed by the DSMB. All other AEs will be reported to these entities at the time of continuing review. A summary of AE data (e.g., frequency, types, and corrective actions) will be provided to the IUPUI IRB, DSMB, CRC Research Subject Advocate, and NIH at the time of continuing review.

Data and Safety Monitoring Board (DSMB)

As we did in our ongoing eIMPACT Trial (see C2), we will form a DSMB to provide independent oversight. None of the DSMB members will be involved in the proposed trial other than serving on this board. The DSMB will consist of a psychiatrist, an endocrinologist, and a clinical trialist from the Indiana University School of Medicine. All AEs that are severe/life-threatening or that raise questions about the risks posed to other participants will be immediately reviewed by the DSMB. In addition, every 6 months, [name] (principal investigator) will submit a written report to the DSMB describing study updates; participant recruitment, accrual, randomization, and retention; treatment delivery and fidelity; data collection and quality; suicidal ideation protection protocol triggers; any adverse events; any protocol deviations; and any IRB amendments. At that time, the DSMB will have a closed meeting to determine whether the trial should continue unchanged, be modified, or be stopped, and the DSMB Chair will provide a written response with all recommendations. The IUPUI IRB, CRC Research Subject Advocate, and NIH will receive copies of all DSMB reports and responses at the time of continuing review.

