B. Innovation

B1. Our trial would be the first to evaluate depression treatment as a diabetes prevention strategy.

This RCT would be the first to test the effect of a depression intervention on A1c in depressed people with prediabetes. Our focus on a psychological factor is a major departure from current prevention efforts.⁵

B2. eIMPACT-DM has innovative aspects that support broader dissemination and implementation.

Although collaborative care for depression in primary care is an established approach,⁵⁷ only one trial⁵⁸ besides our eIMPACT Trial (see C2) has incorporated computerized CBT. Moreover, no trials have used an antidepressant algorithm optimized for diabetes risk reduction. To achieve our long-term goal, large-scale dissemination and implementation must be possible. eIMPACT-DM fits very well in primary care, where behavioral health staff and space are limited, as it harnesses technology to minimize personnel and space requirements. In addition, because eIMPACT-DM uses computerized CBT, it is more scalable, easier to deliver with high fidelity, and likely more cost effective⁵⁹ than current collaborative care models. Finally, eIMPACT-DM can reach patients with logistical barriers, as many components are internet or phone delivered. Pew data show that 89% of adults (87% for non-Hispanic Blacks; 81% for lower income households) use the internet.

B3. Using a statewide information exchange to identify incident T2D is unique and has advantages.

The Indiana Network for Patient Care (INPC),^{60,61} the nation's largest clinical data repository, is a secure statewide health information exchange operated by Regenstrief Institute. In addition to extensive data provided by healthcare systems, INPC gathers data from Indiana Medicaid and commercial payers and death data from the Indiana State Department of Health. Advantages of using INPC seen in our past studies⁶²⁻⁶⁴ are an easily extended follow-up and minimal attrition (no patient participation required).

C. Preliminary Studies

C1. The Beating the Blues for Your Heart Trial (PI: [name]; ClinicalTrials.gov Identifier: NCT01605552)

This small pilot RCT provides initial proof-of-concept data. Although its primary outcome was a CVD risk marker, it allowed for a diabetes-related post hoc analysis. 29 Eskenazi Health

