The exploratory outcome is time to T2D onset, defined as the first occurrence of the following between the participant's enrollment date and five years after their post-treatment visit date: T2D diagnosis (ICD-10 E11), fasting glucose ≥ 126 mg/dL, A1c $\geq 6.5\%$, or death due to T2D. The Regenstrief programmer will identify incident T2D cases by searching INPC – the statewide health information exchange (see B3) – blinded to group assignment. Our endocrinologist ([name]), also blinded, will use standardized criteria to adjudicate all incident T2D cases. As we are doing in the eIMPACT Trial, we will obtain authorization from participants to conduct INPC searches to identify incident diabetes until five years after their post-treatment visit date. We will assess this outcome annually, with the first assessment at post-treatment. Because only a large Phase III trial would be powered for clinical events, incident T2D is an exploratory outcome. Based on our prediabetes inclusion criterion and the review described above,⁷⁰ we expect a diabetes incidence rate of $\geq 25\%$ over 5 years. [name] will use his faculty development funds (\$4K/year) and/or his research account (\$50K) to cover INPC searches after the project period.

Somatic Depressive Symptoms

Total depressive symptoms will be assessed by the 20 depression items (response options: 0-4) of the Symptom Checklist-90 (SCL-20), a reliable and valid scale,¹¹⁵⁻¹¹⁸ at the pre-

and post-treatment visit. Patients with a score ≥ 2 to the hyperphagia item and/or hypersomnia item at pre-treatment will be coded as "yes" for the presence of somatic depressive symptoms. All others will be coded as "no."

Other Factors

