Weight, height, blood pressure, heart rate, respiration rate, and temperature will be measured by CRC nurses (pre, post). Validated questions/scales will assess demographics, medical/psychiatric history, current medications, alcohol use (AUDIT),⁷³ tobacco use (BRFSS Tobacco Use Questionnaire),^{119,120} physical activity (International Physical Activity Questionnaire),¹²¹ OHA adherence (Morisky Medication Adherence Scale-8),¹²²⁻¹²⁴ depressive symptoms (PHQ-9),^{74,75} anxiety (GAD-7),¹²⁵ hostility/anger (Buss-Perry Aggression Questionnaire),⁷⁶ trait positive affect (Positive Affect subscale of the PANAS),^{77,78} life satisfaction (Satisfaction with Life Scale),⁷⁹ insomnia symptoms (Insomnia Severity Index),⁸⁰ sleep quality (PSQI),¹²⁶ eating behaviors (Dutch Eating Behavior Questionnaire),⁸¹ quality of life (SF-20)⁸² (all pre, post), and expectancy of benefit⁸³ (pre). Attention will be determined from the intervention database for eIMPACT-DM patients and from EMR chart review for AC patients (post). Depression care variables (e.g., antidepressant dose/duration and psychotherapy session number/type) will be determined from the treatment delivery database for eIMPACT-DM patients and from EMR chart review for Active Control patients (post). Patients will complete a brief interview to assess depression care received outside of the trial (post). We will assess depression treatment acceptability (post). Diabetes prevention care received outside the trial will be assessed by EMR chart review (post) and a brief interview (post). We will also assess for the occurrence of any potential adverse events using a brief questionnaire and will administered the Techniques for Overcoming Depression Questionnaire⁸⁴ (post).

Type	Name	Time Frame	Brief Description
Hemoglobin A1c	Primary	Baseline, 6 months	The primary outcome is 6-month change in hemoglobin A1c, which will be measured at pre- and post-treatment by an immunoturbidimetric method on a Randox Daytona Clinical Analyzer in the Translation Core Analyte Lab of the Indiana CTSI. A1c is the gold standard glycemic outcome, ¹⁶ a strong predictor of future diabetes development, ^{17,18} and a potent indicator of improvement in clinical diabetes endpoints. ^{8,17,19,20}

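### Record-based safety searches and alerts cover the Eskenazi EMR only; events elsewhere rest on patient self-report, and deaths elsewhere have no stated systematic route

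*Combined protocol and SAP*

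**What the plan says.** Section 9.0 (Adverse Event Monitoring) gives four ways to learn of an event.

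- A record search: events are identified "by conducting Eskenazi Health EMR searches every 6 months (before DSMB meetings) for all emergency department visits, hospitalizations, and deaths that occurred among randomized patients".
- A questionnaire: "reviewing responses on a self-report questionnaire assessing for the occurrence of any potential adverse events since the pre-treatment visit administered at the post-treatment visit". Section 3.0 (Other Factors) also lists it among the post-treatment assessments.
- Alerts: the depression clinical specialist "will also receive alerts through the Eskenazi Health EMR when any randomized patient has a new emergency department visit or hospitalization".
- Volunteered information: "any potential adverse events spontaneously reported by participants (e.g., during a study visit or call) will be evaluated".

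The same section commits to rating all deaths. ED visits and admissions judged unrelated to the study are counted by arm and investigated fully only if the arms look unbalanced.

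Section 1.0 (B3) describes the statewide exchange: "INPC gathers data from Indiana Medicaid and commercial payers and death data from the Indiana State Department of Health". It names as an advantage that follow-up needs no participation by the patient. Section 3.0 (Incident Diabetes) states how the trial will use it: "we will obtain authorization from participants to conduct INPC searches to identify incident diabetes until five years after their post-treatment visit date". Those searches are annual and begin at post-treatment. No section plans an INPC search for adverse events.

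**The concern.** The search is described as covering all ED visits, admissions and deaths among randomised patients, but both record-based routes look into one health system. The other two need a patient who is alive and in contact with the study. The patients least likely to meet that condition are those who have died, are seriously ill or have left the trial, and in them a missed event would matter most.

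What is at stake is the completeness of the counts that the DSMB sees every 6 months when it decides whether the trial continues, changes or stops, and the by-arm comparison that triggers full investigation. A source that could narrow the gap is already in the plan for another purpose.

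**Working it through.** The plan states no figure for completeness of capture, so there is none to reproduce. The check sets the routes side by side and then shows an illustrative size.

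**Step 1. What each route can see**

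| Route | Outside Eskenazi? | Needs the patient? | Deaths? | When |
|---|---|---|---|---|
| EMR search (9.0) | Not stated | No | As recorded in that EMR | Every 6 months |
| EMR alerts (9.0) | Not stated | No | Not named | Real time |
| Questionnaire (3.0, 9.0) | Yes | Yes, at the visit | No | Once, at about month 6 |
| Volunteered reports (9.0) | Yes | Yes, in contact | No | Any contact |
| INPC (1.0 B3, 3.0), not used for safety | Yes | No | State death data | Annually from post-treatment |

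**Step 2. Deaths.** Questionnaire and volunteered reports cannot supply the participant's own death. The alerts do not name deaths. That leaves the EMR search, and nothing says how a death elsewhere would enter that EMR.

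**Step 3. Non-attenders.** Under section 10.0, a patient who leaves because of acute or serious illness has no further study visits or calls, so the questionnaire and the usual occasions for volunteering an event both end. Record data may still be collected with the patient's permission.

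**Step 4. Interim DSMB reviews.** The questionnaire comes 6 months after randomisation, and section 8.0 places the first post-treatment visits in Year 1, Quarter 4. At any 6-monthly review, patients still in treatment have no questionnaire data, whether or not they later drop out.

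**Step 5. Illustrative size.** Let a be the share of patients with no questionnaire and s the share of encounters outside Eskenazi. The share missed by both the EMR search and the questionnaire is m = a × s. This assumes that the EMR shows no outside encounter, that attenders report every one, and that encounter rates do not depend on attendance. The documents give no value for s; 20-50% is an assumption.

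Inputs for a:
- Section 5.0 (Retention Plan): 93% and 91% of the earlier eIMPACT Trial's arms attended at 12 months, so a = 0.07 to 0.09. Of 64 patients that is 0.07 × 64 = 4.5 to 0.09 × 64 = 5.8, or about 4 to 6.
- Section 11.0: at least 50 completers of 64, so up to 64 − 50 = 14, and 14/64 = 0.219. This is slightly above the 20% attrition allowance because the plan rounds 0.80 × 64 = 51.2 down to 50.

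| a | s = 0.20 | s = 0.50 |
|---|---|---|
| 0.07 | 1.4% | 3.5% |
| 0.09 | 1.8% | 4.5% |
| 0.219 | 4.4% | 10.9% |

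For patients still in treatment at an interim review, a = 1, so m equals s whatever the final attrition.

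**The case against.** The strongest reply is that the plan has more contact with patients than the search alone suggests. Section 5.0 promises at least monthly contact in both arms and collects at least two secondary contacts per patient, through whom a death or admission could become known. Section 7.0 gives intervention patients sessions at least every 2 weeks at the start and control patients a call every 4 weeks. The Appendix adds the PHQ-9 suicide item at most study calls, with same-day review when the follow-up questions are positive. The DSMB also receives suicidal-ideation triggers, retention and deviations. And this is a 64-patient pilot of established treatments with no restriction on usual care.

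Much of this stands. It makes an event that escapes every source less likely, and it supports treating the matter as a modest improvement. It does not close the gap: no section says that these contacts ask about adverse events or that secondary contacts are used to find them. Contact frequency at the start also differs by arm, so volunteered reports are an uneven basis for the comparison that triggers full investigation.

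The attrition objection also stands. The 14 non-completers are the most the plan allows for, and the earlier trial lost far fewer, so both ranges are shown.

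**Conclusion.** The point holds as a limited gap in safety ascertainment. Record searches and alerts are confined to the Eskenazi EMR. Admissions and ED visits elsewhere rest on one late questionnaire and on volunteered reports, and deaths elsewhere have no stated systematic route. The illustrative loss is 1.4-4.5% of encounters at the earlier trial's attrition and about 4-11% at 14 of 64. It would be higher if non-attenders have more events. These ranges rest on the assumed 20-50% and are not estimates; the gap for deaths does not depend on them. The A1c analysis is untouched.

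A reader might infer three stronger things that the documents do not support:

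- That adverse events are sought only in the Eskenazi EMR. The questionnaire and volunteered reports are not limited to one provider.
- That an outside death or overdose is certain to go unseen, or that the commitment to rate all deaths cannot be met. Nothing says whether the EMR displays outside encounters or deaths, so the supportable statement is that no route is assured.
- That the authorization must be widened. The form is not available. Section 3.0 mentions incident diabetes, but section 10.0 gives incident diabetes only as an example of the record data to be obtained, so the scope may already be broader.

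**What to change.** In section 9.0:

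1. Add deaths, admissions and ED visits to the INPC search already planned at post-treatment. Cover randomisation to the post-treatment date, for all randomised patients in both arms whether or not they attend; for non-attenders, use the date on which the visit was due.
2. Run the same query before each DSMB report during the treatment phase. These are new pulls, since the planned searches are annual and start at post-treatment.
3. Confirm that the authorization covers this use, and extend it only if it does not.
4. Keep the Eskenazi search and alerts for real-time detection.
5. State whether the Eskenazi EMR shows outside encounters and deaths, and how current the INPC encounter and death data are. If the query is not added, state the limitation in section 9.0.

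The cost is a few extra data pulls with some programmer time, and a few more events to review. The documents give no price per search. No patient visit or procedure is added.

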10.0 Study Withdrawal/Discontinuation

All participants will be considered enrolled at the start of the pre-treatment visit after written informed consent and authorization are obtained. The informed consent statement describes the possibility of and the procedures for withdrawing from the study. A participant may notify either the principal investigator or any member of the research team at any time via email, phone, or in-person that s/he wants to withdraw from the study for any reason. If a participant withdraws before the pre-treatment assessment visit, no payment will be provided.

Other reasons for study withdrawal/discontinuation are: (a) the participant's primary care provider or another provider seeing the participant (e.g., a psychiatrist outside of the study team) no longer believes that the patient is appropriate for this trial after a triggering of the Suicidal Ideation Protection Protocol or any other reason, (b) the participant develops acute or serious illness that precludes completion of the main study visits within the allowed timeframes, and (c) the participant exhibits evidence of a psychotic disorder or bipolar disorder (both of which are exclusionary conditions and could interfere with treatment delivery/effectiveness) during the 6 month treatment phase of the trial. In the case of situation (b), the patient will not complete any future study visits or calls. However, if the patient provides permission, electronic medical record data (e.g., incident diabetes) will still be obtained going forward, consistent with our Authorization Form. In the case of situation (c), patients with a psychotic disorder or bipolar disorder would likely benefit from psychotropic medications, such as antipsychotic medications or mood stabilizer, that are beyond what are provided in this trial.

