Treatment Process. At the end of the pre-treatment visit, our DCS will speak to the patient for 20 minutes via IU Zoom Health to orient them to depression materials and schedule the intake interview. Future DCS contacts will be over the phone or via IU Health Zoom, consistent with patient preference. Our DCS will contact the patient for the intake interview. At meetings every 2 weeks, the DCS will present cases to our team, who will formulate a Step 1 plan with PCP input. The DCS will work with the PCP to implement this plan. Step 1 will be 2 months of psychotherapy or an antidepressant. GDA and PST-PC are our first- and second-line psychotherapies; bupropion and fluoxetine are our first- and second-line antidepressants (others are third-line). For patients on an antidepressant at entry, the dosage may be increased, psychotherapy may be added, or a different antidepressant may be prescribed. For patients who want psychotherapy but have major barriers to GDA, PST-PC will be offered at Step 1. Our DCS will follow patients for 6 months, while monitoring response and staffing cases with the team at least every 2 months. At the start, the DCS will have sessions at least every 2 weeks. For patients who achieve remission ($\geq 50\%$ PHQ-9 reduction and < 3 symptoms⁵⁰), the DCS will develop a relapse prevention plan and follow-up monthly. Step 2 – augmenting Step 1 with psychotherapy or an antidepressant or switching to another psychotherapy or antidepressant – will be delivered to patients not in remission. If remission is not achieved after Step 2, Step 3 will be initiated, which will involve additional psychotherapy and/or antidepressants.

PHQ-9 Score	Action (within 24 hours)
<10 (minimal)	Results will be reported in a note added to the EMR.
10-19 (minor/moderate)	RA will encourage patient to seek treatment at their primary care clinic and will notify the patient's PCP and the embedded behavioral health clinician.
20-27 (severe)	RA will strongly encourage patient to seek treatment at their primary care clinic and will notify the patient's PCP, the embedded behavioral health clinician, and the affiliated psychiatrist.

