Active Control (AC) consists of depression education (study staff), symptom monitoring (study staff), and primary care for depression (clinical staff). (1) At the end of the pre-treatment visit, the RA responsible for Active Control delivery (a clinical psychology PhD mentee of the PI) will speak to the patient for 20 minutes via IU Zoom Health to review depression materials,¹¹⁵ including their PCP's role in its management and treatment options. In addition, patients will be provided with a list of Eskenazi

mental health services, and the RA will encourage patients to follow-up with their PCP. To engender expectancy of benefit, the RA will stress that our notifications should prompt PCP actions and that the available treatments are effective. We will then send an EMR message to the PCP indicating that their patient has a depressive disorder and was randomized to the AC group. This message will encourage the PCP to address their patient's depression, note that there are no care restrictions, and provide the same list of Eskenazi services. (2) The RA will call AC patients every 4 weeks (i.e., at the end of Months 1, 2, 3, 4, and 5) to assess depressive symptoms (PHQ-9) and will notify clinical staff to encourage additional care when indicated (see table). (3) AC patients will receive current primary care for depression. The Eskenazi primary care clinics utilize a team care approach for behavioral health issues, as PCPs are supported by embedded behavioral health clinicians and affiliated psychiatrists available for brief counseling and antidepressant management.

We chose an AC comparator¹¹⁶ for several reasons. (1) Because we plan to use an AC group in the R01-level RCT, we need to use it here to obtain accurate effect size estimates. Other approaches (no comparator or usual care comparator) could overestimate effect sizes. (2) Our AC group will help to ensure that the groups have similar expectancy of benefit and clinical

attention. We will assess expectancy⁸³ and attention and will adjust for them in a sensitivity analysis. (3) Our AC group is feasible. As eIMPACT-DM uses a flexible approach, each patient will have their own treatment path within the intervention structure. Thus, it is not possible to develop a comparator that exactly parallels the attention for each eIMPACT-DM patient.

Type	Name	Description

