11.0 Statistical Considerations

Sample Size Justification and Power Analysis

This pilot RCT is not designed to detect statistically significant differences. We chose N=64, as it is sufficient to yield the expected outcomes and is feasible within the R21 constraints. Assuming an attrition rate of $\leq 20\%$,¹¹⁷ we will have ≥ 50 completers (25/arm). With 50 completers and type I error rate=5%, we will have 55%, 68%, 79%, and 88% power to detect a $d=0.60, 0.70, 0.80$, and 0.90, respectively. We observed a $d=0.90$ for CBT for depression on fasting glucose in depressed primary care patients (see C2).

Primary Aim Analytic Plan

Analyses will use the intent-to-treat approach.¹¹⁸ Tests will be two-tailed with $p<.05$ considered statistically significant. Supplemental analyses of completers and analyses employing multiple imputation (SAS mi and mianalyze) will be performed. We will assess for group differences in baseline factors. Due to randomization, we do not expect differences. Even so, baseline differences will be taken into account when interpreting results, and baseline factors that differ between groups will be added as covariates in sensitivity analyses. We will also add expectancy and attention as covariates in sensitivity analyses.

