potential participant answers “yes” to the clarifying question, the participant will be asked the three suicide questions. If the participant answers “no” to all three suicide questions or if the patient answers “yes” only to Question 3 (previous attempt) and the most recent attempt was \geq 10 years ago, the visit will proceed as normal, and the completed Patient Suicidality Form will be given to the principal investigator. If the participant answers “yes” to any of the three questions (for Question #3 the previous attempt must be within the past 10 years), the research assistant or depression clinical specialist will immediately contact [name]. If [name] cannot be reached, contact [name]. [name] (a clinical psychologist) and [name] (the trial psychiatrist) will review the case as soon as possible, but no later than the same day, to determine the appropriate course of action (e.g., interview the patient to obtain further information, immediately contact the patient’s primary care provider and/or behavioral health clinician to involve them in the decision-making process, consult with clinicians at Sandra Eskenazi Mental Health Center, escort the patient to the Crisis Intervention Unit, and/or contact the police if the patient is at imminent danger of harm and is refusing all care). The depression clinical specialist will also notify the participant’s primary care provider if s/he was not involved in the decision-making process. Regardless of the exact course of action, the study team will ensure that the participant is connected to the appropriate existing clinical services. If the patient’s primary care provider no longer believes that the patient is appropriate for this trial following a situation, s/he will be withdrawn.

Study Calls

Suicidal ideation will be assessed using Item #9 of the PHQ-9 during most study calls completed by the depression clinical specialist responsible for intervention delivery and during most study calls completed by the research assistant responsible for active control delivery.

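### The plan does not secure the 6-month A1c for patients withdrawn on provider judgement or for emerging psychosis or bipolar disorder

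*Combined protocol and SAP*

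**What the plan says.** Section 10.0 places three situations under one label, "Other reasons for study withdrawal/discontinuation are". Situation (a) applies when a provider "no longer believes that the patient is appropriate for this trial after a triggering of the Suicidal Ideation Protection Protocol or any other reason". Situation (b) is acute or serious illness that rules out the main visits. Situation (c) is that "the participant exhibits evidence of a psychotic disorder or bipolar disorder" during the 6-month treatment phase.

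What happens to visits is written for one of the three: "In the case of situation (b), the patient will not complete any future study visits or calls". A provision to keep collecting electronic medical record (EMR) data by permission follows directly. For (c) the section adds only that such patients would likely benefit from psychotropic drugs beyond those the trial provides.

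The Section 16.0 appendix repeats the consequence for (a): if the primary care provider "no longer believes that the patient is appropriate for this trial following a situation, s/he will be withdrawn". It does not mention the post-treatment visit.

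The primary outcome (Section 3.0) is the 6-month change in A1c, assayed in the study laboratory on blood drawn at the pre- and post-treatment visits. Section 11.0 states "Analyses will use the intent-to-treat approach". It specifies a linear mixed model for the two time points, with completer and multiple-imputation analyses as supplements.

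**The concern.** An intent-to-treat comparison needs the outcome of every randomized patient where it can be obtained, including those who stop treatment. In (b), the illness itself rules out the visits. Situations (a) and (c) are not defined that way, so a missing A1c there may be avoidable. Yet the rule written for them is withdrawal from the study, and no sentence keeps the 6-month blood draw. EMR data do not replace it, because the primary outcome is a study-laboratory measurement.

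These patients are unlikely to resemble those who remain. Situation (a) can follow a suicidality trigger. Situation (c) points to a change in medication that the plan itself foresees, and current atypical antipsychotic use is an exclusion at entry (Section 4.0). If their A1c course differs from what their baseline value predicts, the planned analyses miss it. At stake is some bias in an effect estimate that Section 11.0 will judge against a 0.3-point difference (d = 0.50).

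**Working it through.** **1. The plan's own figures.** Section 11.0 assumes attrition of at most 20%: 64 × 0.80 = 51.2, so at least 50 completers holds. For 25 per arm and a two-sided 5% test, the noncentral t distribution gives power of 54.7%, 67.9%, 79.2% and 87.7% at d = 0.60, 0.70, 0.80 and 0.90. The plan states 55%, 68%, 79% and 88%. These reproduce and are not in question.

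**2. What is written for each situation.**

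| Situation | Leaves the study | Visits stop | Data afterwards |
|---|---|---|---|
| (a) provider judgement | yes (10.0, appendix) | not stated | not stated |
| (b) serious illness | yes (10.0) | yes | EMR, by permission |
| (c) psychosis or bipolar disorder | yes (10.0) | not stated | not stated |

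**3. Why the planned methods would not recover the value.** The model has only baseline and 6 months. A withdrawn patient contributes a baseline A1c and nothing between, and the event behind the withdrawal is not in the model. The likelihood analysis therefore relies on missing at random given baseline and arm. The documents describe no imputation model that goes further, and they plan no missing-not-at-random analysis.

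**4. Size of bias.** The documents give no rate for (a) or (c) and no A1c deficit, so both are assumed. Let k1 and k0 be the patients lost in the intervention and control arms (32 each), and let δ be how much worse their true 6-month A1c is than the model predicts, taken as equal in both arms. Then

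bias = (k1 − k0) / 32 × δ.

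| k1, k0 | δ = 0.3 | δ = 0.6 |
|---|---|---|
| 1, 0 | 0.009 | 0.019 |
| 2, 0 | 0.019 | 0.038 |
| 3, 1 | 0.019 | 0.038 |
| 4, 2 | 0.019 | 0.038 |
| 4, 1 | 0.028 | 0.056 |

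This is about 0.01 to 0.06 points. The implied SD is 0.3 / 0.50 = 0.6, so the range is d of about 0.02 to 0.09. The extreme corner, 4 lost against none at δ = 0.6, gives 4/32 × 0.6 = 0.075. For scale, the standard error of a post-treatment difference is about 0.6 × √(2/25) = 0.17.

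**5. Contacts by arm.** Section 7.0 says of the intervention arm "At the start, the DCS will have sessions at least every 2 weeks", with monthly follow-up after remission. Fortnightly sessions over 26 weeks make 26/2 = 13. Fortnightly for 2 months and monthly for the next 4 make 4 + 4 = 8. For control, "The RA will call AC patients every 4 weeks", which is 5 calls. With an assumed trigger probability p per contact, the expected number of patients per 32 with at least one trigger in m contacts is 32 × [1 − (1 − p)^m]:

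| p | m = 5 | m = 8 | m = 13 |
|---|---|---|---|
| 1% | 1.6 | 2.5 | 3.9 |
| 2% | 3.1 | 4.8 | 7.4 |

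At equal p the intervention arm triggers more. If control patients have p = 2% and intervention patients 1%, the figures are 3.1 against 2.5 to 3.9, which is near parity. A trigger leads to withdrawal only if the provider then judges the patient unsuitable.

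**6. Precision.** Retaining 1 to 4 more A1c values in one arm (25 becoming 26 to 29) raises power at d = 0.80 from 79.2% to between 79.9% and 82.0%.

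**The case against.** Three stronger conclusions are tempting, and the documents do not support them.

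- **That the 6-month A1c is lost in (a) and (c).** An end to visits is written for (b) alone, and naming only (b) leaves the other two open. The appendix covers (a), not (c), and does not mention outcome visits. Section 10.0 also refers to the consent statement for withdrawal procedures, and those pages are not available here. Section 3.0 describes authorization for five-year incident-diabetes searches from participants generally, so record-based follow-up may not be confined to (b). What stands is that nothing in the protocol text secures the study-laboratory A1c.
- **That the loss falls mainly on the higher-contact arm.** Item 9 of the PHQ-9 is asked in most calls in both arms, and control providers are also notified of elevated scores. In the predecessor trial, which used a closely similar intervention, attendance at 12 months was 93% in the intervention arm and 91% in usual care. Its response rates of 51% and 20% suggest that triggers per contact could be higher in control. Differential loss is possible but not shown.
- **That the analysis would not be intent-to-treat.** Withdrawn patients stay in the mixed model through their baseline value, so the randomized set is kept. What would be missing is their observed outcome.

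It is also fair to say that the assumed losses are generous. The predecessor's non-attendance from all causes was 7% in the intervention arm, or 0.07 × 32 = 2.2 patients, over twice the duration. The trial is a pilot not designed for significance testing, and Section 11.0 says that the definitive trial's effect size will not rest solely on its results. This limits the consequence. It is not a reason to give up outcomes that could be collected.

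**Conclusion.** The point holds as a gap in outcome retention. For (a) and (c) the written rule is withdrawal from the study, the 6-month A1c has no protection, and the planned missing-data methods would not make good its loss. The bias is probably small: about 0.01 to 0.06 A1c points for a net excess of 1 to 3 of 32 intervention patients at a deficit of 0.3 to 0.6 points, and 0.075 in the most extreme case considered. The upper figure of 0.06 is a fifth of the 0.3-point benchmark and about a third of the standard error. Both the counts and the deficit are assumptions. The bias falls towards zero as control losses approach intervention losses, and it would change sign if control lost more. The change is worth making because it is cheap and serves the plan's own intent-to-treat aim. No view is taken on who should be withdrawn or why.

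**What to change.** Leave the clinical reasons for withdrawal as they are, and add the following.

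- **Section 10.0 and the appendix:** patients who meet (a) or (c), still consent, and whose provider does not object to the visit are invited to the 6-month A1c and HOMA visit and analysed as randomized. EMR data collection continues by permission, as already written for (b). Align the consent and authorization wording if it does not already say this.
- **Reporting:** withdrawals by reason and arm, with the number whose 6-month A1c was obtained.
- **Section 11.0:** a simple missing-not-at-random sensitivity analysis within the multiple imputation already planned. Shift the imputed 6-month A1c of withdrawn patients by a fixed delta, for example 0.3 and 0.6 points, in the intervention arm alone and in both arms, and report how the treatment effect moves. Set a corresponding shift for HOMA on its own scale.

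The cost is a wording amendment, a short extra analysis, and somewhat more follow-up effort for a few visits that are already planned.
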